## **5.6 Rescue Medications & Supportive Care**

Subjects should receive appropriate supportive care measures as deemed necessary by the treating investigator. Suggested supportive care measures for the management of AEs with potential immunologic etiology are outlined in Section 5.2.3.2, [Table 6](#). Where appropriate, these guidelines include the use of oral or IV treatment with corticosteroids, as well as additional anti-inflammatory agents if symptoms do not improve with administration of corticosteroids. Note that several courses of steroid tapering may be necessary as symptoms may worsen when the steroid dose is decreased. For each disorder, attempts should be made to rule out other causes such as metastatic disease or bacterial or viral infection, which might require additional supportive care. The treatment guidelines are intended to be applied when the investigator determines the events to be related to study treatment.

Note: If after evaluation of the event, it is determined not to be related to MK-1248 and/or pembrolizumab, the investigator does not need to follow the treatment guidance.

It may be necessary to perform conditional procedures such as bronchoscopy, endoscopy, or skin photography as part of the evaluation of the event.

## **5.7 Diet/Activity/Other Considerations**

### **5.7.1 Diet**

Subjects should maintain a normal diet unless modifications are required to manage AEs such as diarrhea, nausea or vomiting.

### **5.7.2 Contraception**

MK-1248 and pembrolizumab may have adverse effects on a fetus in utero. Furthermore, it is not known if either drug has transient adverse effects on the composition of sperm. Non-pregnant, non-breast-feeding women may be enrolled if they are considered highly unlikely to conceive. Highly unlikely to conceive is defined as 1) surgically sterilized, or 2) postmenopausal (a woman who is  $\geq 45$  years of age and has not had menses for greater than 1 year will be considered postmenopausal), or 3) not heterosexually active for the duration of the study. The 2 birth control methods can be either 2 barrier methods or a barrier method plus a hormonal method to prevent pregnancy.

The following are considered adequate barrier methods of contraception: diaphragm, condom (by the partner), copper intrauterine device, sponge, or spermicide. Appropriate hormonal contraceptives will include any registered and marketed contraceptive agent that contains an estrogen and/or a progestational agent (including oral, subcutaneous, intrauterine, or intramuscular agents).

Subjects should be informed that taking the study medication may involve unknown risks to the fetus (unborn baby) if pregnancy were to occur during the study. In order to participate in the study they must adhere to the contraception requirement (described above) for the duration of the study and during the follow-up period defined in Section 7.2.2-Reporting of Pregnancy and Lactation to the Sponsor. If there is any question that a subject will not reliably comply with the requirements for contraception, that subject should not be entered into the study.

### **5.7.3 Use in Pregnancy**

If a subject inadvertently becomes pregnant while on treatment with MK-1248 or pembrolizumab, the subject will immediately be removed from the study. The site will contact the subject at least monthly and document the subject's status until the pregnancy has been completed or terminated. The outcome of the pregnancy will be reported to the SPONSOR without delay and within 24 hours if the outcome is a serious adverse experience (e.g., death, abortion, congenital anomaly, or other disabling or life-threatening complication to the mother or newborn). The study investigator will make every effort to obtain permission to follow the outcome of the pregnancy and report the condition of the fetus or newborn to the SPONSOR. If a male subject impregnates his female partner the study personnel at the site must be informed immediately and the pregnancy reported to the SPONSOR and followed as described above and in Section 7.2.2.

### **5.7.4 Use in Nursing Women**

It is unknown whether MK-1248 or pembrolizumab is excreted in human milk. Since many drugs are excreted in human milk, and because of the potential for serious adverse reactions in the nursing infant, subjects who are breast-feeding are not eligible for enrollment.

## **5.8 Subject Withdrawal/Discontinuation Criteria**

Subjects may withdraw consent at any time for any reason or be dropped from the trial at the discretion of the investigator should any untoward effect occur. In addition, a subject may be withdrawn by the investigator or the Sponsor if enrollment into the trial is inappropriate, the trial plan is violated, or for administrative and/or other safety reasons. Specific details regarding discontinuation or withdrawal procedures; including specific details regarding withdrawal from Future Biomedical Research, are provided in Section 7.1.4 – Other Procedures.

In this trial, a subject may discontinue from treatment but continue to participate in the regularly scheduled activities, as long as the subject does not withdraw consent. Discontinuation from treatment is permanent. Once a subject has discontinued treatment, even though he/she continues to be monitored in the trial, he/she shall not be allowed to begin treatment again.

Note: Subjects who discontinue treatment for reasons other than PD will have post-treatment follow-up for disease status until PD, initiating a non-study cancer treatment, withdrawing consent, or becoming lost to follow-up.

A subject must be discontinued from the trial for any of the following reasons:

- The subject or legal representative (such as a parent or legal guardian) withdraws consent.
- Confirmed disease progression

A subject must be discontinued from treatment (but may continue to be monitored in the trial) for any of the following reasons:

- The subject withdraws consent for treatment
- Confirmed disease progression
- Unacceptable adverse events (See Dose Modification Section 5.2.3)
- Intercurrent illness that prevents further administration of treatment
- Investigator's decision to withdraw subject
- Subject has confirmed positive serum pregnancy test
- Noncompliance with study treatment or procedure requirements
- Administrative reasons
- Completed treatment as defined in this protocol

[Click here to enter text.](#)

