## 1.0 TRIAL SUMMARY

Abbreviated Title	Phase 1 Trial of MK-1248 as Monotherapy and in Combination with Pembrolizumab in Subjects with Advanced Solid Tumors
Trial Phase	Phase 1
Clinical Indication	Treatment of subjects with advanced solid tumors
Trial Type	Interventional
Type of control	None
Route of administration	Intravenous
Trial Blinding	Unblinded Open-label
Treatment Groups	Subjects will be allocated by non-random assignment to one of 2 treatment arms: Arm 1: MK-1248 as monotherapy Arm 2: MK-1248 in combination with pembrolizumab
Number of trial subjects	Approximately 96 subjects will be enrolled.
Estimated duration of trial	The sponsor estimates that the trial will require approximately 4 years from the time the first subject signs the informed consent until the last subject's last visit.
Duration of Participation	Each subject will participate in the trial from the time the subject signs the Informed Consent Form (ICF) through the final contact. After a screening phase of up to 28 days, each subject will be allocated by non-random assignment into one of two arms and receive treatment with MK-1248 alone or in combination with pembrolizumab. Study treatment in both arms will begin on Day 1 of each 3-week cycle. For subjects enrolled in Arm 1 and Arm 2, treatment with MK-1248 will end after 4 cycles; treatment with pembrolizumab in Arm 2 will continue for up to 24 months. Treatment in both arms will continue until disease progression, unacceptable adverse event(s), intercurrent illness that prevents further administration of treatment, Investigators decision to withdraw treatment, subject withdraws consent, pregnancy of the subject, noncompliance with study treatment or procedure requirements, subject completes treatment, or administrative reasons requiring cessation of treatment. After the end of treatment, each subject will be followed for 30 days for adverse event monitoring (serious adverse events will be collected for 90 days after the end of treatment, or 30 days after the end of treatment if the subject initiates new anticancer therapy, whichever is earlier).

Enrollment into this study has been prematurely discontinued due to program prioritization and not related to any safety concerns. The cut-off date for enrollment is 31-Mar-2017.

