Treatment in Arm 2, (MK-1248 in combination with pembrolizumab) will begin once 2 subjects complete 1 cycle of  $\geq 3$  mg dose level in Part A, and will follow a 3+3 design to identify a preliminary MTD in Part D. The starting dose of MK-1248 will be 0.12 mg and the dose of 200 mg pembrolizumab will be used in Arm 2. During 3+3 dose escalation, at least 2 days of observation will occur between each of the first 3 subjects at each dose level. There will be a one week observation period between the first and second subject treated with the combination in the first cohort of Arm 2. Dose confirmation in Part E will refine the estimate of tolerability of the MTD using a toxicity probability interval.

Enrollment to both arms will occur in parallel with treatment allocation accomplished by non-random assignment to Arm 1 or Arm 2 using an interactive voice response system/integrated web response system (IVRS/IWRS). Doses of MK-1248 used in combination will be at least 1-2 dose levels behind the monotherapy dose, and would not exceed the MTD for monotherapy. However, once the MTD or RP2D (recommended Phase 2 dose) for the monotherapy arm is established, the dose of MK-1248 in combination may continue escalation up to that dose.

The trial will be conducted in conformance with Good Clinical Practices.

Adverse Events (AEs) will be evaluated according to criteria outlined in the National Cancer Institute's (NCI) Common Terminology Criteria for Adverse Events (CTCAE), version 4.0.

[figure not shown]
Specific procedures to be performed during the trial, as well as their prescribed times and associated visit windows, are outlined in the Trial Flow Chart - Section 6.0. Details of each procedure are provided in Section 7.0 – Trial Procedures.

Enrollment into this study has been prematurely discontinued due to program prioritization and not related to any safety concerns. The cut-off date for enrollment is 31-Mar-2017. Subjects who are ongoing in the study after that date and who do not yet meet established protocol discontinuation criteria, as outlined in Section 5.8, will continue to attend study visits and be followed per protocol. Subjects who are ongoing in the study after that date and who do not yet meet established treatment discontinuation criteria, as outlined in Section 5.8, may continue to receive study treatment per protocol, provided the investigator feels such treatment is in the best interest of the subject.

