All adverse events that occur after the consent form is signed but before randomization/treatment allocation must be reported by the investigator if they cause the subject to be excluded from the trial, or are the result of a protocol-specified intervention, including but not limited to washout or discontinuation of usual therapy, diet, placebo treatment or a procedure. From the time of randomization/treatment allocation through 30 days following cessation of treatment, all adverse events must be reported by the investigator. Such events will be recorded at each examination on the Adverse Event case report forms/worksheets. The reporting timeframe for adverse events meeting any serious criteria is described in section 7.2.3.1. The investigator will make every attempt to follow all subjects with non-serious adverse events for outcome.

Electronic reporting procedures can be found in the EDC data entry guidelines. Paper reporting procedures can be found in the Investigator Trial File Binder (or equivalent).

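### Section 5.8 makes confirmed progression both a mandatory exit from the trial and a treatment stop with monitoring allowed; read literally, the exit conflicts with the post-treatment safety windows

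*Combined protocol and SAP*

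**What the plan says.** Section 5.8 of the protocol has two lists. The first is headed "A subject must be discontinued from the trial for any of the following reasons" and has two entries: withdrawal of consent and confirmed progression. The second is headed "A subject must be discontinued from treatment (but may continue to be monitored in the trial) for any of the following reasons" and also contains confirmed progression. The same section says that "a subject may discontinue from treatment but continue to participate in the regularly scheduled activities, as long as the subject does not withdraw consent". Its note on disease follow-up reads: "Subjects who discontinue treatment for reasons other than PD will have post-treatment follow-up for disease status until PD".

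The enrolment-closure note (Sections 1.0 and 2.1, and repeated elsewhere) relies on both lists. Ongoing subjects "who do not yet meet established protocol discontinuation criteria, as outlined in Section 5.8, will continue to attend study visits", while those "who do not yet meet established treatment discontinuation criteria, as outlined in Section 5.8, may continue to receive study treatment per protocol".

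The safety sections make no exception for progression:
- Section 1.0: "After the end of treatment, each subject will be followed for 30 days for adverse event monitoring".
- Section 7.2 sets the AE reporting period from allocation "through 30 days following cessation of treatment, all adverse events must be reported by the investigator".
- Section 7.1.8.3.1 makes a Safety Follow-Up Visit mandatory at about 30 days after the last dose, or before new antineoplastic treatment if that comes first.
- Sections 7.2.3.1 and 7.2.3.2 require SAEs and ECIs to be reported for 90 days after treatment ends, or 30 days if new anticancer therapy starts.

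**The concern.** One event cannot both compel exit from the trial and leave monitoring open. The point has practical force because the closure note makes continued study visits depend on the Section 5.8 criteria. A site that follows the exit entry to the letter cannot also meet the 30-day and 90-day duties for a subject whose progression is confirmed inside those windows.

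Section 8.6.2 plans summaries of AEs, SAEs and immune-related AEs. If sites apply the exit entry, late events go uncollected selectively in subjects with confirmed progression. If sites differ, ascertainment differs by site. Section 5.2.3.1 says that immune-mediated events can appear several months after the last dose. That bears only on the 90-day SAE/ECI window, because new non-serious AEs beyond 30 days are not collected under either reading.

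**Working it through.** The plan gives no figure for follow-up lost, so there is none to reproduce. The check has three steps.

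**1. What is covered if a subject exits at confirmed progression.** Section 7.1.7.1 moves the final-visit activities to the day of exit and requires AEs already present to be followed. Section 7.2.3.1 requires related SAEs to be reported at any time once the investigator learns of them. Section 7.1.8.4 keeps survival contact open. Not covered are AEs that begin after exit, and SAEs or ECIs that are judged unrelated or are not volunteered.

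**2. Days per subject under the exit reading.** Inputs:
- Dosing is on Day 1 of each 21-day cycle (Section 5.2): Days 1, 22, 43, 64, 85, 106.
- MK-1248 ends after four cycles (Section 1.0), so the last Arm 1 dose is no later than 1 + 3×21 = Day 64. Pembrolizumab continues in Arm 2.
- Imaging is every 9 weeks from first dose (Section 7.1.2.6): 1 + 63 = Day 64, then Day 127.
- Progression is confirmed at least 4 weeks later (Sections 4.2.3.1 and 7.1.2.7.1): 64 + 28 = Day 92, or 127 + 28 = Day 155.
- Clinically stable subjects may be dosed while confirmation is awaited (Section 7.1.2.7.1).

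Assumptions: treatment ceases at the last dose, and there are no dose delays or unscheduled scans.

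Let g = day of confirmation − day of last dose. AE days lost = max(0, 30 − g). SAE/ECI days lost = max(0, 90 − g), or max(0, 30 − g) if new therapy starts (in brackets).

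| Case | Last dose | Confirmed | g | AE days lost | SAE/ECI days lost |
|---|---|---|---|---|---|
| Arm 2, dosed while awaiting confirmation | 85 | 92 | 7 | 23 | 83 (23) |
| Either arm | 64 | 92 | 28 | 2 | 62 (2) |
| Either arm | 43 | 92 | 49 | 0 | 41 (0) |
| Arm 2, confirmed at next scheduled scan | 106 | 127 | 21 | 9 | 69 (9) |
| Either arm, confirmed at next scheduled scan | 64 | 127 | 63 | 0 | 27 (0) |
| Either arm, confirmed at next scheduled scan | 43 | 127 | 84 | 0 | 6 (0) |
| Arm 1, progression on second scan | 64 | 155 | 91 | 0 | 0 (0) |

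These are not bounds. Section 5.2.5 allows dosing up to 5 days late. A Day 85 dose given on Day 90 has g = 92 − 90 = 2, losing 28 AE days and 88 (28) SAE/ECI days. A Day 64 dose given on Day 69 has g = 92 − 69 = 23, losing 7 and 67 (7).

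**3. The primary endpoint.** DLTs are counted over the first 21 days. Confirmation by repeat imaging needs at least 28 days after the first sign of progression, so this exit cannot fall within the DLT period.

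**The case against.** The best case on the other side is that the documents already show what is meant. Section 7.1.2.7.1 ends study therapy at confirmed progression and says nothing of leaving the trial. Section 7.1.7.1 encourages subjects who stop treatment early to attend all remaining visits. Section 7.2.3.1 requires deaths from any cause to be reported in the post-treatment window, and treats progression as an AE when it leads to hospitalization or death, so it expects to hear about subjects who progress. Section 5.7.3 keeps monthly contact with a subject removed from the study for pregnancy, so removal need not end safety contact. The safety windows run from the end of treatment, not from trial status. All of this stands as evidence of intent. It does not remove a mandatory entry, and it does not cover events that begin after exit.

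The objection also limits the size. The 23- and 83-day figures need an Arm 2 subject dosed at the investigator's discretion a week before confirmation. The 2-day AE loss in Arm 1 is nominal, because the safety visit has a window of ±7 days. Clinically unstable subjects do not need confirmatory imaging, so the exit entry need not be triggered for them.

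A reader might infer three stronger points, none of which the documents support:
- **That the safety tables will be biased.** No progression rate is given and site practice is unknown, so neither a number of subjects nor a bias can be stated.
- **That Section 7.1.8.2 confirms the exit reading, because it follows subjects until progression.** That sentence stands under the treatment period and mirrors the treatment-stop reasons in Section 1.0. Taken literally it would also end follow-up at an unacceptable AE, contrary to Sections 5.8 and 7.1.8.3.1.
- **That the 3- and 6-month pharmacokinetic and antibody samples are lost through Section 5.8.** Whether subjects who progress owe those samples is a separate question, between Section 7.1.8.3.2 and the flow-chart footnotes.

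**Conclusion.** The contradiction is certain from the text of Section 5.8, and the closure note makes it operative. Its likely effect is modest. Continued safety follow-up is probably intended, so data are at risk only where a site applies the exit entry, and then only the events left uncovered at exit.

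With no dose delays and confirmation at the 4-week minimum after the first scan, the Arm 2 example loses 23 AE days and 83 SAE/ECI days (23 with new therapy). Arm 1 loses at most 2 and 62 (2) under those assumptions. Many cases lose no AE days. DLT assessment, MTD decisions and survival contact are not affected. The text should be corrected, but the point does not call the trial's primary conclusions into question.

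**What to change.** Reconcile the two lists in Section 5.8 with Sections 1.0, 7.1.2.7.1, 7.1.7.1, 7.1.8.3.1, 7.2, 7.2.3.1 and 7.2.3.2. The text should state that the existing collection windows apply to subjects with confirmed progression unless consent is withdrawn: 30 days for AEs, and 90 days for SAEs and ECIs, or 30 if new anticancer therapy starts. This concerns data collection only and changes no treatment rule.

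The cost is a wording edit. The visit and the reporting windows already exist, so no new assessment is added. The downside is slightly longer safety follow-up for subjects who progress, at sites that now release them at confirmation. Enrolment closed on 31-Mar-2017, so the gain is confined to subjects still ongoing.

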## **5.9 Subject Replacement Strategy**

A subject who discontinues from the trial will not be replaced except as described in Section 5.2.4 Replacement of Subjects During DLT Evaluation Period.

## **5.10 Beginning and End of the Trial**

The overall trial begins when the first subject signs the informed consent form. The overall trial ends when the last subject completes the last study-related phone-call or visit, discontinues from the trial or is lost to follow-up (i.e. the subject is unable to be contacted by the investigator).

## **5.11 Clinical Criteria for Early Trial Termination**

There are no pre-specified criteria for terminating the trial early.

## 6.0 TRIAL FLOW CHART

Note: Enrollment into this study has been prematurely discontinued due to program prioritization and not related to any safety concerns. The cut-off date for enrollment is 31-Mar-2017. Subjects who are ongoing in the study after that date and who do not yet meet established protocol discontinuation criteria, as outlined in Section 5.8, will continue to attend study visits and be followed per protocol. Subjects who are ongoing in the study after that date and who do not yet meet established treatment discontinuation criteria, as outlined in Section 5.8, may continue to receive study treatment per protocol, provided the investigator feels such treatment is in the best interest of the subject.

	Screening Phase	Treatment Phase Cycle = 21 days													End of Treatment	Post Treatment Phase				
Treatment Cycle/Title	Screening (Visit 1)	Cycle 1						Cycles 2-4 						Cycles 5 and 6 (Arm 2 only) 	Cycle 7 and Beyond (Arm 2 only) 	Discon	Safety Follow-up	Follow-up		
Cycle Day		1	2	3	5	8	15	1	2	3	5	8	15	9 weeks after 1 st dose	1	1		30 days after last dose	3 and 6 months after last dose	Every 9 weeks until PD
Scheduling Window (Days)	-28 to -1				+/- 3	+/- 3	+/- 3				+/- 3	+/- 3	+/- 3	+/- 7	+/- 7	+/- 7	+/- 7	+/- 7	+/- 7	
Administrative Procedures																				
Informed Consent 	X																			
Informed Consent for Future Biomedical Research 	X																			
Inclusion/Exclusion Criteria	X																			
Subject Identification Card	X																			
Demographics and Medical History	X																			
Concomitant Medication Review	X	X	X			X	X	X	X			X	X		X	X	X	X		
Prior Oncology Treatment	X																			

Treatment Cycle/Title	Screening Phase	Treatment Phase Cycle = 21 days														End of Treatment	Post Treatment Phase			
		Cycle 1							Cycles 2-4 								Cycles 5 and 6 (Arm 2 only) 	Cycle 7 and Beyond (Arm 2 only) 	Discon	Safety Follow-up
Cycle Day	Screening (Visit 1)	1	2	3	5	8	15	1	2	3	5	8	15	9 weeks after 1 st dose	1	1		30 days after last dose	3 and 6 months after last dose	Every 9 weeks until PD
Scheduling Window (Days)	-28 to -1				+/- 3	+/- 3	+/- 3				+/- 3	+/- 3	+/- 3	+/- 7			+/- 7	+/- 7	+/- 7	
History																				
MK-1248 Drug Administration (Arms 1 & 2) 		X						X												
Pembrolizumab Drug Administration (Arm 2 only) 		X						X						X	X					
Clinical Procedures/Assessments																				
Adverse Events Monitoring	X	X	X	X		X	X	X	X	X		X	X	X	X					
Full Physical Examination	X	X 						X 						X 	X 	X	X	X		
Height	X																			
Weight	X	X						X						X	X	X	X			
Vital Signs (temperature, pulse, respiratory rate, blood pressure) 	X	X	X	X		X	X	X	X	X		X	X	X	X					
12-Lead Electrocardiogram 	X	X 						X 												
ECOG Performance Status	X	X 						X 						X 	X 	X	X			
Tumor Imaging and irRECIST Response Assessment 	X													X	X	X			X	
Survival Status 		<																	>	

Treatment Cycle/Title	Screening Phase (Visit 1)	Treatment Phase Cycle = 21 days														End of Treatment	Post Treatment Phase		
		Cycle 1							Cycles 2-4 								Cycles 5 and 6 (Arm 2 only) 	Cycle 7 and Beyond (Arm 2 only) 	Discon
Cycle Day		1	2	3	5	8	15	1	2	3	5	8	15	9 weeks after 1 st dose	1	1	30 days after last dose	3 and 6 months after last dose	Every 9 weeks until PD
Scheduling Window (Days)	-28 to -1				+/- 3	+/- 3	+/- 3				+/- 3	+/- 3	+/- 3	+/- 7	+/- 7	+/- 7	+/- 7	+/- 7	+/- 7
Laboratory Procedures/Assessments –Analysis by Local Lab																			
CBC with differential	X 	X 	X			X	X	X 				X	X		X 	X 	X	X	
C Reactive Protein	X 	X 	X			X	X	X 				X	X		X 				
PT/INR and aPTT	X 																		
Chemistry Panel	X 	X 	X			X	X	X 				X	X		X 	X 	X	X	
LDH, GGT	X 	X 						X 							X 				
Pregnancy Test – Urine or Serum β-hCG, if applicable 	X	X 																	
Immunoglobulins (IgA, IgG, IgM)		X 						X 							X 				
Urinalysis	X 																		
Thyroid Function (T4, T3, TSH) 		X 						X 							X 	X 	X		
HIV, Hepatitis B and C 	X																		

Treatment Cycle/Title	Screening Phase	Treatment Phase Cycle = 21 days														End of Treatment	Post Treatment Phase			
		Cycle 1							Cycles 2-4 								Cycles 5 and 6 (Arm 2 only) 	Cycle 7 and Beyond (Arm 2 only) 		
Cycle Day	Screening (Visit 1)	1	2	3	5	8	15	1	2	3	5	8	15	9 weeks after 1 st dose	1	1		30 days after last dose	3 and 6 months after last dose	Every 9 weeks until PD
Scheduling Window (Days)	-28 to -1				+/- 3	+/- 3					+/- 3	+/- 3	+/- 3	+/- 7			+/- 7	+/- 7	+/- 7	
Laboratory Procedures/Assessments-Analysis to be Performed by Central Lab																				
Humoral Immunity Assays 		X 						X							X					
Cytokine Panel 		X 	X	X				X	X	X					X					
Anti-MK-1248 Antibodies (Arms 1 & 2) 		X 	X	X			X	X	X	X	X		X	X			X	X		
Pharmacokinetics for MK-1248 (Arms 1 & 2) 		X 	X	X	X (require for 4 lowest dose levels in Arm 1)	X	X	X	X	X	X (require for 4 lowest dose levels in Arm 1)	X	X		X		X	X		
Anti-MK-3475 Antibodies (Arm 2 only) 		X	X	X		X	X	X	X	X		X	X		X	X	X	X		
Pembrolizumab/MK-3475 PK (Arm 2 only) 		X	X	X		X	X	X	X	X		X	X		X	X	X	X		
Blood for DNA Correlative Studies 		X						X												

Treatment Cycle/Title	Screening Phase	Treatment Phase Cycle = 21 days														End of Treatment	Post Treatment Phase		
		Cycle 1							Cycles 2-4 								Cycles 5 and 6 (Arm 2 only) 	Cycle 7 and Beyond (Arm 2 only) 	
Cycle Day	Screening (Visit 1)	1	2	3	5	8	15	1	2	3	5	8	15	9 weeks after 1 st dose	1	1	30 days after last dose	3 and 6 months after last dose	Every 9 weeks until PD
Scheduling Window (Days)	-28 to -1				+/- 3	+/- 3	+/- 3				+/- 3	+/- 3	+/- 3	+/- 7	+/- 7	+/- 7	+/- 7	+/- 7	
Blood for RNA Correlative Studies 		X						X											
Blood for Genetic Analysis 		X																	
Tumor Tissue Collection 	X																		
Post Treatment Tumor Biopsy 						X													
Pharmacodynamic (receptor availability flow cytometry assay (Arms 1 & 2)  )	X	X 	X	X (require for MK-1248 dose levels <30mg)	X (require for 4 lowest dose levels in Arm 1)	X	X	X	X	X (require for MK-1248 dose levels <30mg)	X (require for 4 lowest dose levels in Arm 1)	X	X	X					

1. Trial treatment may be administered up to 3 days before or 5 days after the scheduled Day 1 of each cycle, beginning in Cycle 3. Cycle 2 Day 1 may be administered up to 5 days after the scheduled Day 1.
2. Written consent must be obtained prior to performing any protocol specific procedure. Tests performed prior to the subject signing consent as part of routine clinical management are acceptable in lieu of a screening test if performed within the specified time frame.
3. Signing the informed consent for future biomedical research (FBR) is optional, and may be signed at any time during the subject's participation in the trial. Detailed instructions for the collection and management of FBR specimens are provided in the Procedure Manual.
4. The Sponsor recommends that all subjects be prophylactically pre-medicated with 8 mg dexamethasone, intravenously, 1000 mg acetaminophen, orally, and 10 mg loratadine, orally, 1.5 hours ( $\pm$ 30 minutes) before infusion with MK-1248.
5. In the Arm 2, pembrolizumab is administered first, then following a 30-minute interval, MK-1248 will be administered.

6. These samples and procedures required predose Day 1 may be performed up to 72 hours prior to dosing.
7. Vital signs (VS) to include temperature, pulse, respiratory rate and blood pressure. On Day 1 of Cycles 1-4 in Arm 1 and Arm 2, collect prior to dosing, at 2-hr, 4-hr and 6-hr after start of the MK-1248 infusion. In Arm 2, beginning with Cycle 5, collect VS prior to pembrolizumab dosing on Day 1 of each cycle.
8. 12-lead ECG should be performed at screening for all subjects and repeated in Arm 1 prior to and within 30 minutes after the end of the MK-1248 infusion in Cycles 1-4.
9. Tumor imaging (CT scan or MRI) should be performed within 28 days of enrollment. Tumor imaging and response assessment to be performed 9 weeks after first dose, than every 9 weeks until disease progression. Imaging assessments should be repeated every 9 weeks and follow calendar days and should not be adjusted for delays in Cycle starts or extensions of dosing frequencies. The same imaging technique should be used on a subject throughout the trial. Scans used for tumor measurements may be requested for central review.
10. Upon Sponsor request, participants may be contacted for survival status at any time during the course of the study.
11. Laboratory tests at Screening are to be performed within 7 days prior to the first dose of study treatment.
12. In Arm 1 and Arm 2, on Day 1 in cycles 1-4, CBC with differential, CRP and chemistry profile should be drawn prior to dosing and repeated 4 hours after the start of the MK-1248 infusion, with results of the CBC and chemistry profile reviewed by the PI or appropriate designee before the subject is discharged from the clinic. In Arm 2, beginning with Cycle 5, CBC with differential, CRP and chemistry profile should be drawn prior to dosing.
13. For women of reproductive potential, a urine pregnancy test will be performed at Screening and within 24 hours prior to the first dose of study treatment. If a urine pregnancy test cannot be confirmed as negative, a serum pregnancy test is required.
14. Thyroid function testing is to be performed starting in Cycle 1 and then every other cycle and at the Post treatment safety follow-up visit
15. Include HCV, RNA (qualitative) or Hepatitis C antibody, HBsAg, and HIV type 1 and type 2 (e.g., HIV-1/2 antibody screening test and evaluation of HIV viral load as needed).
16. Collect humoral immunity assays prior to dosing in Cycles 1-4 in Arm 1 and Cycles 1-6 in Arm 2 (specific assays designated in procedures manual).
17. For Arm 1, collect cytokine panels for cycles 1-4 on day 1 predose, 1 hour and 4 hours post infusion, and on day 2 and day 3. For Arm 2, collect cytokine panels for cycles 1-4 on day 1 predose, 1 hour and 4 hours post infusion, and on day 2 and day 3. For Cycles 5 and 6, collect samples on day 1 Predose, 1hour and 4 hour post infusion.
18. MK-1248 Anti-drug antibody (ADA) will be drawn in Arm 1, predose MK-1248 on Day 1, Day 2, Day 3, Day 8 and Day 15 of Cycles 1-4, and at the Safety visit 30 days post discontinuation and at 3 months and 6 months after the last dose . In Arm 2 MK-1248 ADA will be obtained predose MK-1248 on Day 1, on Day 2, Day 3, Day 8 and Day 15 of Cycles 1-4, predose pembrolizumab Cycles 5, and 6, and at the Safety visit 30 days post discontinuation and at 3 months and 6 months after the last dose .
19. MK-1248 Pharmacokinetic (PK) samples will be drawn in each cycle on Day 1 predose MK-1248, at the end of the MK-1248 infusion (+ 10 minutes), 2h after the start of the MK-1248 infusion (+/- 10 minutes), and on Day 2, Day 3, Day 5, Day 8, and Day 15 and at the Safety visit 30 days post discontinuation and at 3 months and 6 months after the last dose for subjects treated at the 4 lowest dose levels in Arm 1. Starting at the 30 mg dose in Arm 1 and all dose levels in Arm 2, PK samples will be drawn in each cycle on Day 1 predose MK-1248, at the end of MK-1248 infusion (+ 10 minutes), 2h after the start of the MK-1248 infusion (+/- 10 minutes), on Day 2, Day 3, Day 8, and Day 15 in Cycles 1-4 and the Safety visit 30 days post discontinuation and at 3 months and 6 months after the last dose. In addition, in Arm 2, MK-1248 PK will be drawn predose pembrolizumab in Cycles 5, and 6. If the sample day falls on a weekend or holiday, please consult the sponsor for alternate sample collection times.
20. Pembrolizumab Anti-drug antibody (ADA) will be drawn in Arm 2 at the following timepoints: predose pembrolizumab on Day 1, on Day 2, Day 3, Day 8 and Day 15 in Cycles 1-4, predose in Cycles 5, 6, 8 and every 4 cycles thereafter, and at the Safety visit 30 days post discontinuation and at 3 months and 6 months after the last dose.
21. Pembrolizumab Pharmacokinetic (PK) samples will be drawn in Arm 2, Cycles 1-4 Day 1 predose pembrolizumab, at the end of the Pembrolizumab infusion (+10 minutes) at the end of MK-1248 infusion (+ 10 minutes), 2h after the start of the MK-1248 infusion (+/- 10 minutes), and on Day 2, Day 3, Day 8, and Day 15, predose in Cycles 5, 6, 8 and every 4 cycles thereafter, at the Safety visit 30 days post discontinuation and at 3 months and 6 months after the last dose.. If the sample day falls on a weekend or holiday, please consult the sponsor for alternate sample collection times.

22. Blood for correlative studies (RNA and DNA samples) will be drawn prior to dosing on Cycle 1 Day 1 and prior to dosing on Cycle 2 Day 1 or Cycle 1 Day 22 for subjects who do not receive a second dose of MK-1248. Detailed instructions for the collection and management of these samples are provided in the Procedure Manual.
23. This sample should be drawn for planned analysis of the association between genetic variants in DNA and drug response. If there is either a documented law or regulation prohibiting collection, or if the IRB/IEC does not approve the collection of the sample for these purposes, then this sample will not be collected at that site. If the sample is collected, leftover extracted DNA will be stored for future biomedical research if the subject signs the FBR consent. If the planned genetic analysis is not approved, but FBR is approved and consent is given, this sample will be collected for the purpose of FBR
24. Tumor tissue (archival or newly obtained biopsy) will be required at Screening in Parts B, C, D, and E. Leftover tissue may also be saved for future biomedical research if the subject signs the Future Biomedical Research consent.
25. Post treatment tumor biopsy is optional, but strongly encouraged in Parts B, C, D, and E, in Cycle 1 between Day 8 and Day 15. Leftover tissue may also be saved for future biomedical research if the subject signs the Future Biomedical Research consent.
26. In Arm 1, blood sample for pharmacodynamic (PD) will be drawn in Screening, in Cycles 1-4 on Day 1 pre-dose MK-1248, at the end of MK-1248 infusion (+ 10 minutes), 2h after the start of the MK-1248 infusion (+/- 10 minutes), on Day 2, Day 8, and Day 15; on Day 3 dose level <30 mg, Day 5 required for 4 lowest dose levels. In case of DLT, starting at the 5th dose level in Arm 1, PD samples will be drawn in Screening, in Cycles 1-4 on Day 1 pre-dose MK-1248, at the end of the MK-1248 infusion (+ 10 minutes), 2h after the start of the MK-1248 infusion (+/- 10 minutes), on Day 2, Day 3, Day 8, and Day 15. For all dose levels in Arm 2, PD samples will be drawn at screening , in Cycles 1-4 on Day 1 pre-dose pembrolizumab, at the end of the MK-1248 infusion (+ 10 minutes), 2h after the start of the MK-1248 infusion (+/- 10 minutes), on Day 2, Day 3, Day 8, and Day 15. In Arm 2, Day 5 will not be drawn for any dose levels. Day 3 will be drawn for MK-1248 doses <30 mg. In addition, in Arm 2 PD samples will be drawn pre-dose pembrolizumab in Cycles 5-6.

